6.5 Urine Drug and Alcohol Screen

The urine drug screen should be completed, and results known before any efficacy assessments are conducted at baseline and all post-baseline clinic visits. Subjects should refrain from taking alcohol during the study after the first administration of SM. The urine drug screen will be performed as point-of-care (POC) testing with POC kits provided to study site(s).

If a subject has a positive drug screen or tests positive for ethanol at baseline or any post-baseline clinic visits (days 1, 4, and 7), then the subject should be withdrawn from the study and no efficacy assessments (HAM-D₆, MADRS, and CGI-S) should be performed at that visit. All safety assessments should still be performed. The subject should receive a follow-up phone call approximately 1 week following discontinuation from the study.

6.7 Pharmacodynamic Blood Sampling

Separate, additional blood draws will be collected to measure BDNF concentrations. Six blood samples (2.0 mL each) will be collected at clinic visits on days 1, 4, and 7, as follows:

- Pre-dose (within 60 minutes of SM administration)
- 4 hours (\pm 30 minutes) following SM administration

One blood sample (2.0 mL) will be collected at the clinic visit on Day 10 approximately 72 hours after SM administration on Day 7.

- 72 hours (\pm 60 minutes) following SM administration

7 STUDY VARIABLES AND ASSESSMENTS

All clinical outcome assessments will be collected using paper scales/questionnaires.

7.1 Rater Qualification Process

Identified raters from each study site will be asked to provide information regarding their highest degree of education, field of study, study indication and scale administration experience, and previous certifications using a rater qualification form provided by the Sponsor. Based on the information entered on the qualification form and accompanying certificates, the Sponsor or Sponsor's designee will determine if raters are qualified to administer scales or require Sponsor provided training. Raters can appeal their qualification status; final determination will be made by the Sponsor. All qualified study coordinators, investigators, and designees must complete the Sponsor rater trainings.

A site will be considered activated once at least one rater per scale training is completed. Investigators from recent previous Supernus Pharmaceutical Inc. studies will be considered as qualified raters.

An attempt will be made to have the same qualified rater administer the same scales (efficacy) throughout the study for each subject.

7.1.1 Hamilton Depression Rating Scale – 6 Items

The Hamilton Depression Rating Scale is one of the most widely used clinician-administered depression scales ([Hamilton 1960](#); [Williams 1988](#)). The original version contains 17 items related to symptoms of depression over the past week developed for hospital inpatients. The HAM-D₆ derived from the original 17-item version of the scale offers sensitivity for measuring severity of detecting improvement of depression comparable to other more complex versions ([O'Sullivan 1997](#)).

Five of the 6 items (Depressed Mood, Low Self-Esteem and Guilt, Social Life Activities/Interests, General Psychomotor Retardation, and Psychic Anxiety) are scored on a scale of 0 to 4, and 1 item (Tiredness and Pains) is scored on a scale of 0 to 2, for a possible total score of 0 to 22.

The scale is a clinician-reported outcome (ClinRO) administered by a qualified rater at all clinic visits, and it will be administered remotely on days 2, 3 5, 6, 8, and 9 to subjects while at home.

7.1.2 Montgomery-Åsberg Depression Rating Scale

The MADRS is a 10-item investigator-rated diagnostic questionnaire used to measure the severity of depressive episodes in patients with mood disorders and is designed to be sensitive to changes brought on by treatment ([Montgomery 1979](#)). Each question is scored from 0 to 6, the sum of the 10 subtests score will yield a total score ranging from 0 to 60. A higher MADRS score indicates more severe depression.

Successful therapy is indicated by a lower total score in subsequent testing (Montgomery-Åsberg Depression Rating Scale Past Week [Follow-Up Evaluation]).

There are 10 subtests based on each item:

1. Reported sadness
2. Apparent sadness
3. Inner tension
4. Reduced sleep
5. Reduced appetite
6. Concentration difficulties
7. Lassitude
8. Inability to feel
9. Pessimistic thoughts
10. Suicidal thoughts

The rater will use a structured interview that standardizes the administration of the 10 MADRS items known as structured interview guide for the MADRS, a structured interview was developed by [name] and [name] in order to increase inter-rater reliability, thus improving signal detection ([Williams 2008](#)).

The Standard (including comparison to euthymic baseline for 3 items) and Past Week versions will be administered, with the Standard Version administered at screening and the Past Week Version administered on days 1, 4, 7, and 10. Euthymic baseline is auto populated based on the information captured at the first administration.

The scale is a ClinRO administered by a qualified rater at all clinic visits.

7.1.3 Clinical Global Impression – Severity of Illness

The CGI scale was developed to provide a brief, stand-alone assessment of the clinician's view of a subject's global functioning prior to and after administration of SM ([Guy 1976](#)). The CGI-S is a single-item, clinician rating of the clinician's assessment of the severity of symptoms in relation to the clinician's total experience with patients with MDD. The CGI-S is evaluated on a 7-point scale, where:

- 1=Normal, not at all ill, asymptomatic
- 2=Borderline ill
- 3=Mildly ill
- 4=Moderately ill
- 5=Markedly ill
- 6=Severely ill
- 7=Extremely ill

Successful therapy is indicated by a lower overall score in subsequent testing.

The scale is a ClinRO administered by a qualified rater at all clinic visits.

7.2 Safety Variables and Assessments

Safety assessments include monitoring, evaluation, and recording of all concomitant medications and AEs, and the evaluation of clinical laboratory test results, vital sign measurements, body weight, 12-lead ECGs, C-SSRS, CADSS, BPRS+, and the performance of physical examinations as detailed in the Schedule of Events and Assessments ([Table 1](#)).

The investigator is responsible for monitoring the safety of subjects who have entered this study and for alerting the Sponsor or its designee to any event that seems unusual, even if this event may be considered an unanticipated benefit to the subjects.

7.2.1 Adverse Events

As defined by the ICH Guideline for Good Clinical Practice (GCP), an AE is any untoward medical occurrence in a patient or clinical investigation subject administered a pharmaceutical product and which does not necessarily have to have a causal relationship with treatment.

An AE can be, for example:

- Any unfavorable and unintended sign (including an abnormal laboratory finding), symptom, or disease temporally associated with the use of a medicinal product, whether or not considered related to the medicinal product.
- Any new disease, intercurrent injuries, or exacerbation of an existing disease.
- Any deterioration in a laboratory value or other clinical test (e.g., ECG) that results in symptoms, a change in treatment, or discontinuation from SM.
- Recurrence of an intermittent medical condition (e.g., headache) not present at baseline.

Surgical procedures are not AEs; they are therapeutic measures for conditions that require surgery. The condition for which the surgery is required is an AE, if it occurs or is detected during the study.

7.2.2 Adverse Events of Special Interest

At the current time, no adverse events of special interest have been identified. This section will be updated when new information becomes available.

7.2.3 Overdose

No data are available. Should an overdose of SPN-820 be administered or ingested, the subject should be closely monitored for adverse signs and symptoms and appropriate supportive medical care administered.

7.2.4 Causality

AEs may be categorized as either adverse drug reactions (ADRs) or suspected adverse drug reactions (SADRs) based on their relationship to SM and the degree of certainty about causality.

SADRs are a subset of AEs for which there is evidence to suggest a causal relationship between the SM and the AE (i.e., there is a reasonable possibility that the SM caused the AE).

ADRs are a subset of all SADRs for which there is reason to conclude that the SM caused the event.

7.2.5 Recording and Evaluation of Adverse Events

All subjects who are screened will be questioned regarding any current and prior medical health status or diagnoses and any medical records will be documented as medical history. At each contact with the subject following the first administration SM on Day 1, The investigator must seek information on AEs by specific questioning and, as appropriate, by examination.

Information on all AEs should be recorded immediately in the source document, and also in the appropriate AE module of the eCRF. All clearly related signs, symptoms, and abnormal diagnostic procedure results should be recorded in the source document, though they may be grouped under one diagnosis. For example, fever, elevated white blood cell count, cough, abnormal chest X-ray, etc., can all be reported as “pneumonia.”

All AEs occurring after administration of SM throughout the study must be recorded. A TEAE is defined as an AE with a start date on or after the first dose of SM administration, or that worsened following first administration of SM. All AEs in this study will be recorded after administration of SM, therefore all will be considered TEAEs. The clinical course of each AE should be followed for at least 30 days following the date of last administration of SM (either due to EOS or ET) or until resolution, or until, in the medical judgment of the investigator, the event has stabilized or is assessed as chronic.

The investigator is responsible for evaluating AEs and determining the following:

- Serious versus non-serious: Is the event a serious adverse event (SAE)?
- Causality: Was the AE related or not related to the SM?
- Severity: How pronounced is the incapacity/discomfort caused by an AE?

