3.1.2 Secondary Objectives

- To evaluate the safety and tolerability of SPN-820 administered once every 3 days for a 7-day treatment period in adults with MDD.

■ [REDACTED]

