4.6. Study Treatment Exposure

Duration of exposure for each subject is defined as:

- Duration of Treatment Exposure = date of last dose – date of first dose + 1.

The number (%) of subjects been dosed at each visit and the duration of exposure (days) will be summarized descriptively. A listing of treatment exposure will also be provided.

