8.1. Adverse Events

All adverse events (AEs) will be coded using the MedDRA v26.1. The MedDRA version used for reporting will be specified in the footnote of the applicable output.

A treatment-emergent adverse event (TEAE) is defined as an AE with a start date on or after the date of the first dose of study medication, or that worsened in severity following the first dose of study medication. Any event that is present at baseline but worsens in severity will be determined by the Investigator and entered in the CRF as new AE. Thus, all eCRF-collected AEs that occurred on or after the date of the first dose of study medication are TEAEs.

Based on the Investigator's determination, the severity of TEAEs will be classified as mild, moderate or severe. For summaries by severity, a subject experiencing multiple AEs in the same preferred term with different intensities will only be counted once with the maximum severity. If severity is missing, then the maximum severity will be assumed for the analysis (i.e., severity = severe).

The relationship between the study medication and a TEAE is determined by the Investigator and will be classified as unrelated (i.e., unlikely related and not related) or related (possibly related and definitely related). TEAEs with missing relatedness will be counted as definitely related. For summaries by relationship, a subject experiencing multiple AEs in the same preferred term with different relationship will only be counted once with the most related occurrence.

An overview of TEAE will include summaries of number and percent of subjects who had at least one TEAE, Treatment-emergent serious AE (SAE), Treatment-emergent SAEs related to SM, TEAE leading to death, TEAE by maximum severity, TEAE by relationship, and TEAE leading to withdrawal of study medication.

In addition to the overview of TEAE summary, the following TEAEs summary tables will be provided:

- Treatment-Emergent Adverse Events by System Organ Class and Preferred Term
- Most Common ($\geq 5\%$) Treatment-Emergent Adverse Events by Preferred Term
- Treatment-Emergent Adverse Events by System Organ Class, Preferred Term, and Severity
- Treatment-Emergent Adverse Events by System Organ Class, Preferred Term, and Relationship to Study Medication
- Treatment-Emergent Serious Adverse Events by System Organ Class and Preferred Term
- Treatment-Emergent Adverse Events Leading to Withdrawal of Study Medication by System Organ Class and Preferred Term

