- A data listing of death will be provided. If no death occurred, a blank listing with “No subject died on this study.” will be presented.

A subject with multiple occurrences of an AE will be counted only once in the AE category per SOC and PT for summary tables. The sorting will be based on the decreasing frequency.

Listing will be provided for all AEs, SAE, and TEAE Leading to Withdrawal of Study Medication.

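### SAP 8.1 plans no TEAE summary by dosing interval, so the planned tables cannot show whether acute adverse events fade, recur or accumulate after the doses on Days 4 and 7

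*Protocol*

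**What the plan says.** The secondary objective (Protocol 3.1.2) reads "To evaluate the safety and tolerability of SPN-820 administered once every 3 days for a 7-day treatment period". Protocol 5.2 and SAP 2.3 fix the doses on Days 1, 4 and 7.

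Protocol 7.2.5 and SAP 8.1 both anchor treatment-emergence to the first dose. The protocol says "A TEAE is defined as an AE with a start date on or after the first dose of SM administration", and the SAP states that "all eCRF-collected AEs that occurred on or after the date of the first dose of study medication are TEAEs". For counting, SAP 8.1 says "A subject with multiple occurrences of an AE will be counted only once in the AE category per SOC and PT for summary tables", and for severity that "a subject experiencing multiple AEs in the same preferred term with different intensities will only be counted once with the maximum severity". The tables it lists are an overview, TEAEs by SOC and PT, common TEAEs by PT, by severity, by relationship, serious TEAEs, and TEAEs leading to withdrawal of study medication. None is by dose, dosing interval, onset day or recurrence.

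The inputs for a by-dose table exist:

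- Protocol Table 1 and Section 6.2.1 schedule AE review on each of Days 1 to 10 and at the follow-up call.
- SAP 8.1 plans a listing of all AEs.
- SAP 4.6 tabulates the number and percentage of "subjects been dosed at each visit" and lists exposure.

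**The concern.** This is an intermittent regimen with three separate exposures. The TEAEs that Protocol 2.4 reports as most frequent include dizziness, nausea, headache and somnolence, which could plausibly follow each dose. Among the completed studies described there, subjects with TRD received a single 2400 mg dose, so repeated dosing at that level in patients is something this trial adds. A reader of the study report will want to know whether a symptom seen after Day 1 returns after Days 4 and 7.

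The planned AE tables have no time dimension, although AEs are the most frequently reviewed safety data in the trial. Laboratory values, vital signs, weight, ECG, C-SSRS, CADSS and BPRS+ are all summarised by visit (SAP 8.2 to 8.5, 8.7 and 8.8). A subject with dizziness after all three doses adds the same one count as a subject with dizziness after the first dose only.

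**Working it through.** The plan gives no figure to reproduce here: the sample size rests on clinical judgment, and no AE rate is assumed. The check applies the SAP 8.1 counting rule to assumed patterns.

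**Inputs.** Three doses (SAP 2.3); 50 subjects, the planned enrolment (Protocol 8.2), all assumed to receive every dose; one preferred term, with one AE record per affected subject per dose (assumed).

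**Rule.** Planned entry = subjects with the term after any dose ÷ 50.

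| Pattern | Affected after dose 1 / 2 / 3 | AE records | Planned entry | Rate after dose 1 | Rate after dose 3 |
|---|---|---|---|---|---|
| Fades | 15 / 0 / 0 | 15 | 15/50 = 30% | 15/50 = 30% | 0/50 = 0% |
| Recurs, same subjects | 15 / 15 / 15 | 45 | 15/50 = 30% | 15/50 = 30% | 15/50 = 30% |
| Declines, later cases among the first 15 | 15 / 8 / 3 | 26 | 15/50 = 30% | 15/50 = 30% | 3/50 = 6% |
| Accumulates, earlier cases among the final 15 | 3 / 8 / 15 | 26 | 15/50 = 30% | 3/50 = 6% | 15/50 = 30% |
| New onsets, different subjects | 5 / 5 / 5 | 15 | 15/50 = 30% | 5/50 = 10% | 5/50 = 10% |

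The planned entry is the same in all five rows, whereas the three per-dose rates differ between every pair of rows.

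**How a by-dose table could mislead if built carelessly.**

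- *Unequal windows.* Days 1–3 and 4–6 are 3 days each. Day 7 to the call on Day 12 (+2) is 12 − 7 + 1 = 6 to 14 − 7 + 1 = 8 days. Longer observation alone could look like accumulation. Days 7–9 restore equal length.
- *Survivor denominators.* The plan expects about 50 enrolled and 40 completing, so 50 − 40 = 10 may be lost. Suppose 15/50 have the event after dose 1, 10 of those 15 leave before dose 3, and the other 15 − 10 = 5 have it every time. The rate falls from 15/50 = 30% to 5/40 = 12.5%, although nobody who stayed improved. In the fixed cohort of 40 it is 5/40 = 12.5% at both doses.
- *Onset-only counting.* An event lasting from Day 1 through Day 7 would appear in the first window only.
- *Imputed dates.* SAP Table 3 sets a missing start day to the first dose date when month and year match and the event does not end before that date. Uncertain events therefore move into the first window.

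**Precision.** At an assumed 20% incidence, exact (Clopper-Pearson) 95% intervals are 10.0% to 33.7% for 10/50 and 9.1% to 35.6% for 8/40.

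**The case against.** The strongest reply is that the plan already answers its stated objective. That objective concerns the regimen over a 7-day period, and no objective or endpoint asks about change between doses. Incidence over the whole regimen, with severity, withdrawal, discontinuation and numbers-dosed tables, is a legitimate tolerability summary. The study is open-label, descriptive and without hypotheses, and per-dose rates would be imprecise. All of this stands, and it limits the point to an improvement.

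A reader might infer four stronger things, which the documents do not support:

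- *That the trial cannot show the pattern.* AEs are sought on each of Days 1 to 10, and AE and exposure listings are planned. With about 50 subjects, the pattern could largely be reconstructed from them. What is missing is a summary with a per-dose denominator.
- *That the first-dose TEAE definition is the fault.* It only decides whether an event is treatment-emergent. A by-dose table would use the same definition.
- *That early leavers dilute later-dose rates.* No later-dose rate is planned, so none is diluted. Early leavers matter only for how an added table is built.
- *That no planned table supports a tolerability conclusion.* Several do, at regimen level.

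What remains is that a listing is not an incidence table, and none of the planned tables separates the patterns above.

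**Conclusion.** The point holds as a gap in the SAP 8.1 table list. For a three-dose intermittent regimen, the planned TEAE tables cannot distinguish fading, recurrence and accumulation: in the illustration, patterns with dose-3 rates from 0% to 30% share one entry of 30%. Those counts are assumed and show only what the counting rule hides; they do not predict any result. The point is a cheap improvement, not an error in the plan, and it calls for no change to Protocol 7.2.5, the visit schedule or the overall tables.

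Two limits of the data would remain. The documents describe AE start dates but no onset times, so an event starting on Day 4 or Day 7 cannot be ordered against that day's dose. SAP 8.1 gives a new-record rule for worsening only for events present before treatment ("Any event that is present at baseline but worsens in severity will be determined by the Investigator and entered in the CRF as new AE"), so how worsening of an ongoing event after a later dose is recorded is not stated.

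**What to change.** Keep the overall tables and add one descriptive table to SAP 8.1:

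1. TEAE incidence, for any TEAE and by PT, in equal windows after each dose: Days 1–3, 4–6 and 7–9. Show events from Day 10 to the follow-up call separately.
2. Count each subject once per window, with subjects who received that dose as the denominator.
3. Repeat the table in subjects who received all three doses, so that loss of intolerant subjects is not read as fading.
4. Count an event as present in every window in which it is ongoing. Show new onsets, and the number of subjects with recurrence, separately.
5. Flag events whose start dates were imputed under SAP Table 3.

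Footnote the table to say that onsets on Days 4 and 7 cannot be placed before or after that day's dose, and that per-dose rates are descriptive and imprecise.

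The cost is one extra table from data already collected, with no new visits or assessments.

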7.2.6 Criteria for Assessing Severity

The investigator will evaluate the comments of the subject and the response to treatment in order that he or she may judge the true nature and severity of the AE. Severity refers to the accumulated intensity of discomfort/impairment of health since the last recording of an AE and will be assessed according to the following criteria:

- **Mild:** Awareness of sign, symptom, or event, but easily tolerated.
- **Moderate:** Discomfort is enough to interfere with usual activity and may warrant intervention.
- **Severe:** Incapacitating with inability to do usual activities or significantly affects clinical status and warrants intervention.

The criteria for assessing severity are different from those used for seriousness.

7.2.7 Criteria for Assessing Causality

The investigator is responsible for determining the relationship between the administration of SM and the occurrence of an AE as not suspected or as a suspected reaction to SM, as defined below:

Not suspected: The temporal relationship of the AE to SM administration makes a causal relationship unlikely, or other drugs, therapeutic interventions, or underlying conditions provide a sufficient explanation for the observed event.

- Not related: Temporal relationship to SM administration is missing or implausible, or there is an evident other cause.
- Unlikely related: Temporal relationship to SM administration makes a causal relationship improbable; and other drugs, chemicals, or underlying disease provide plausible explanations.

Suspected: The temporal relationship of the AE to SM administration makes a causal relationship possible, and other drugs, therapeutic interventions, or underlying conditions do not provide a sufficient explanation for the observed event.

- Possibly related: Temporal relationship to SM administration is plausible, but concurrent disease or other drugs or chemicals could also explain event. Information on drug withdrawal may be lacking or unclear. This event will be reported as a SADR.
- Definitely related: Temporal relationship to SM administration is plausible, and concurrent disease or other drugs or chemicals cannot explain event. The response to withdrawal of the medication (dechallenge) should be clinically plausible. The event must be definitive pharmacologically or phenomenologically, using a satisfactory rechallenge procedure if necessary. This event will be reported as an ADR.

